15.0 Recruitment Methods

15.1 Describe when, where, and how you will recruit potential subjects:

All participants will be recruited from the Virginia Tech, NRV, and Roanoke Valley communities.

All participants will be recruited using participant lists from the VT Center for Gerontology, email listservs to VT and the VT Life Long Learning Institute, emailing advertisements to senior centers and senior living communities, newspaper advertisements, word-of-mouth, and visits to local community organizations.

15.2 Describe the source of subjects (for example, clinic patients with specific conditions, students in the library, community members at a gathering, or members of a local gym):

University or community members

15.3 Describe the methods that you will use to identify potential subjects:

21-1072 Validation and application of wearable sensors for capturing responses to losses of balance

Please see question 15.1.

15.4 Describe materials that you will be use to recruit subjects. Attach copies of these documents with this protocol in Protocol Management and be sure to include the IRB protocol number on each document.

- *For flyers, attach the final copy of printed flyers.*
- *For Virginia Tech News, Facebook postings and ads, newspaper ads, websites, MTurk/SONA/online survey systems, etc., attach the final wording and graphics to be used.*
- *For email recruitments, please include the subject line.*
- *For advertisements meant for audio broadcast, please submit the wording of the advertisement prior to taping (to avoid having to re-record with approved language) and submit the final recorded version for IRB review before use.*
- *Describe any compensation to subjects. Separate compensation into appropriate categories, such as: reimbursement for expenses, time and effort, and additional incentives for study participation. For each category, specify the amount (including any pro-rated amount), schedule, and method of payment.*

Flyers are included with this application. This same language will be used in recruitment emails (subject line = Research volunteers needed) and newspaper advertisements.

Compensation is provided for time and effort. Participants will be compensated \$10 for each balance training session, \$20 for each balance testing session, and \$50/week of wearing the sensors. For participants traveling to Blacksburg from at least 25 miles away, an extra \$10 per session will be provided to offset high gasoline prices. Payment will be provided weekly.

If a participants withdraws from the study early, then they will be paid \$10/hour for time completed, and \$50 per week completed of wearing the sensors (as long as they completed at least one half of the week prior to withdrawing).

All payments will be made in the form of cash.

16.0 Withdrawal of Subjects

16.1 Describe circumstances under which you anticipate subjects could be withdrawn from the research without their consent:

Participants can be withdrawn if they fail to follow the investigator instructions during sessions or miss scheduled sessions.

16.2 If applicable, describe any procedures for orderly termination (e.g., discontinuation of a study drug or debriefing after a behavioral intervention):

N/A

16.3 Describe procedures that you will follow when subjects withdraw from the research, including partial withdrawal from procedures with continued data collection (e.g., participant declines to continue with regular blood draws, but continues with periodic behavioral questionnaires):

All sessions and data collections will be terminated when a participant withdraws from the study. Partial withdraw will not be accommodated, meaning that participants cannot withdraw from some of the procedures but remain involved in others.

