8.0 Procedures Involved

8.1 Describe and explain the study design:

For our primary objective, a one-group repeated-measures design will be used to validate the use of wearable sensors to capture responses to LOBs. Non-balance training participants will use wearable sensors for three weeks to capture responses to naturally-occurring trips and slips during daily life. Subjects will then complete a laboratory session to capture lab-induced LOB responses simultaneously from the wearable sensors and a gold-standard optoelectronic motion capture system.

For our secondary objective, a three-group posttest-only design will be used to compare the effects of three balance training exercises on responses to LOBs after laboratory-induced trips and slips, and two weeks of naturally-occurring real-world trips and slips. Balance training participants will first complete three weeks of their assigned training. Subjects will then complete a laboratory session to capture lab-induced LOB responses simultaneously from the wearable sensors and a gold-standard optoelectronic motion capture system. Subjects will then use wearable sensors for two weeks to capture responses to naturally-occurring trips and slips during daily life.

8.2 Provide a description of:

- *All research procedures being performed*
- *If the study has more than one procedure, session, and/or subject population, describe each procedure, session, and/or study*

population separately. For complex studies, you are encouraged to include a figure or chart.

Recruitment and Informed Consent

- Interested participants will respond to our recruitment strategies and contact the investigators.
- The investigators will telephone interested participants and follow the telephone script included in the application to first screen participants for inclusion criteria. If participants satisfy the inclusion criteria, the investigator will continue the telephone conversation and administer the health questionnaire described in an attachment to this application. De-identified information from this health questionnaire will then be reviewed by a health professional with specialist training for the geriatric population. This specialist will be a board certified physician or board certified specialist in geriatric physical therapy.

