- If the participant passes the health questionnaire, then a DEXA assessment for osteoporosis will take place. This assessment will be based upon a DEXA scan performed for this study, or DEXA scan completed within the last year.
- If a DEXA scan is performed for this study, the scan will take place in the Human Integrative Physiology Lab, led by [name]. [name] does not have a role in the current work, but his lab will be providing this service to the PI for a fee. The Human Integrative Physiology Lab is in the Garvin Innovation Building in the CRC ([name]). A member from the research team involved in this IRB application will meet the subject at this location to provide a lead. Trained staff in this lab will conduct the scan.
- If the participant passes the DEXA scan, she/he will have completed our screening process.
- A copy of the informed consent form will be delivered to the participant, and the first visit will be scheduled (at least 24 hours after delivery of the informed consent form).
- The investigator will meet the participant in our research lab. The investigator will confirm the inclusion criteria and ask if they have any questions about the informed consent form. All questions will be answered. If the participant still wants to participate, they will sign the informed consent form, and be provided a copy for them to keep.

Group Assignment and Training

- Participants will be randomly assigned to be either a non-balance training participant or a balance-training participant. Balance training participants will then be assigned to either TT, NT, or ST.
- If the participant is assigned to balance training, this training will be completed twice a week for three weeks. Each training session will be approximately 45 minutes in duration. The details of each type of training is described in detail in section 7.1.
- NT, TT, and ST will all be customized to participants' capabilities, and training difficulty will progressively increased based on participants' capabilities. For NT, difficulty will be increased by 1) adding the obstacle to training during all four phases, 2) leaning the participant farther forward during Phase 3, and asking subjects to walk faster during Phase 4. For TT, difficulty will be increased by increasing the maximum speed of the treadmill perturbations. For ST, difficulty will be increased by using heavier ankle

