14.0 Number of Subjects

14.1 Indicate the total number of subjects to be enrolled and how this number was determined (e.g., sample size calculation [show], number of available subjects in a finite pool, number of tests funding award would allow):

60 participants will be enrolled. This number is based upon a formal sample size analysis described here:

30 non-balance training participants will be recruited for our primary objective. Given that this objective is for validation, no formal effect sizes could be determined. Rather, we estimated 30 participants for this objective to be a reasonable number based upon our available resources and the number of expected LOBs estimated from prior work [Handelzalts et al. 2020].

30 balance training participants will be recruited for our secondary objective and be based upon Hypothesis 3: NT and TT participants will exhibit improved LOB responses after lab-induced trips and slips compared to ST participants.

The sample size was determined using data from lab-induced trips among community-dwelling older adults aged 65 years or older (Pavol et al., 2001). The effect size index (i.e., Cohen's $d = 1.45$) was determined using the difference in mean trunk angle from vertical at the time of recovery foot ground contact between fallers and non-fallers (17.4°) and the combined standard deviation (12°). The difference in means was considered the minimal clinically important difference based on the anchor-based method (Rai et al., 2015). Using G*Power (Faul et al., 2007) for an independent t-test with 80% power and a one-sided Type I error (or alpha) of 5%, a sample size of seven participants per group is needed. In an effort to be conservative and account for any participants withdrawing from the study, 10 participants per balance training group (TT,NT,ST) will be recruited.

Handelzalts, S., N.B. Alexander, N. Mastruserio, L.V. Nyquist, D.M. Strasburg, and L.V. Ojeda. Detection of Real-World Trips in At-Fall Risk Community Dwelling Older Adults Using Wearable Sensors. *Front Med*, 2020. 7: p. 514.

14.2 If this is a multi-site study, indicate the number of subjects to be enrolled at this site and the total to be enrolled from all sites:

21-1072 Validation and application of wearable sensors for capturing responses to losses of balance

Not a multi-site study.

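### Balance training participants removed for missed sessions lose the lab test, so Hypotheses 3 and 4 drift toward adherent completers to the extent the rule is used

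*Combined protocol and SAP*

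**What the plan says.** Section 16.1, on withdrawal without the participant's consent, reads: "Participants can be withdrawn if they fail to follow the investigator instructions during sessions or miss scheduled sessions". It does not say how many missed sessions count.

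Section 16.3 gives the consequence: "All sessions and data collections will be terminated when a participant withdraws from the study". It adds: "Partial withdraw will not be accommodated, meaning that participants cannot withdraw from some of the procedures but remain involved in others".

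Section 8.1 fixes when the outcome is measured. "Balance training participants will first complete three weeks of their assigned training"; the laboratory session follows, and two weeks of sensor wear come last. Section 8.2 says "this training will be completed twice a week for three weeks", which is 2 × 3 = 6 sessions. Section 8.1 describes the design as "a three-group posttest-only design will be used to compare the effects of three balance training exercises on responses to LOBs". On allocation, Section 8.2 says "Balance training participants will then be assigned to either TT, NT, or ST".

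Section 5.2 plans a one-way ANOVA and Dunnett's test against ST for Hypothesis 3, and an equivalence test of NT against TT for Hypothesis 4. It names no analysis population, missing-data method or sensitivity analysis.

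Section 14.1 calculates seven per group and recruits ten, in part to "account for any participants withdrawing from the study, 10 participants per balance training group".

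**The concern.** Missing a training session happens after assignment and may depend on the training received. The arms make different demands: Section 7.1 describes up to 40 sudden treadmill perturbations per TT session and unannounced release from a lean in NT, against strength and graded standing-balance exercises in ST. Less able or more apprehensive participants might miss more sessions in one arm than another. If they are then removed, they contribute nothing to Hypothesis 3 or 4.

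Loss of that kind from NT or TT would favour the result that Hypothesis 3 predicts; loss from ST would work against it. Without a pre-training balance-response measure, the analysis can neither show how the lost participants differed on the outcome scale nor adjust for it. The decision to remove is also a judgement with no written criterion, and the documents describe no blinding of those who make it.

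**Working it through.** **1. The passages side by side.** Outcome after six sessions (8.1, 8.2) + removal allowed for missed sessions (16.1) + all data collection ended and no partial participation (16.3) = no Hypothesis 3 or 4 outcome for anyone removed during training. No other section brings such a participant back for testing.

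**2. The plan's sample size.** Section 14.1 gives a difference of 17.4°, SD 12°, 80% power, one-sided 5% and an independent t-test.
- d = 17.4 / 12 = 1.45.
- The noncentral t calculation gives n = 6.68, rounded up to 7 per group. The stated figure reproduces.
- Power of this test is 81.9% at 7 per group and 92.9% at 10. The reserve is 3 of 10 per arm.

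**3. Size of selective loss (assumptions, not document figures).** Suppose an arm of 10 loses its m least adherent members, and low adherence correlates r with a worse outcome. If r = 1, the mean of those who remain improves by 0.171, 0.317 or 0.456 SD for m = 1, 2 or 3 (simulation). For other values, shift = r × that figure, and degrees = shift × 12.

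| m removed | r = 0 | r = 0.3 | r = 0.5 |
|---|---|---|---|
| 1 | 0 | 0.3 × 0.171 = 0.05 SD | 0.5 × 0.171 = 0.09 SD |
| 2 | 0 | 0.3 × 0.317 = 0.10 SD | 0.5 × 0.317 = 0.16 SD |
| 3 | 0 | 0.3 × 0.456 = 0.14 SD | 0.5 × 0.456 = 0.23 SD |

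The range for r = 0.3 to 0.5 is 0.05 × 12 = 0.6° to 0.23 × 12 = 2.8°. Against the planning difference this is 0.6 / 17.4 = 3% to 2.8 / 17.4 = 16%. With no true effect and loss from one perturbation-training arm only, the simulated one-sided error of a two-sample t-test rises from 5% to between 6.2% and 11.9%.

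**4. Power under Dunnett's test.** Section 5.2 does not state sidedness, so both are shown. For each contrast the noncentrality is 1.45 / √(1/n₁ + 1/n₀), with n₁ the trained arm, n₀ ST, and degrees of freedom equal to total n − 3.

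| n per arm | Noncentrality | df | Power, one-sided | Power, two-sided |
|---|---|---|---|---|
| 10, 10, 10 | 1.45 / √(1/10 + 1/10) = 3.24 | 27 | 89% | 81% |
| NT or TT at 7, others 10 (contrast of the reduced arm) | 1.45 / √(1/7 + 1/10) = 2.94 | 24 | 82% | 72% |
| 7, 7, 7 | 1.45 / √(1/7 + 1/7) = 2.71 | 18 | 75% | 63% |

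**5. Sensor wear.** In Section 8.1, balance training participants have the lab test before sensor wear, so stopping the sensors does not cost them the Hypothesis 3 or 4 outcome. Non-balance-training participants wear sensors for three weeks first. For them, stopping wear can, under 16.3, cost the later lab test, which serves Hypotheses 1 and 2.

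**The case against.** The strongest reply has four parts.

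- **The rule is optional.** Section 16.1 permits removal and does not require it, and 16.3 speaks of a participant withdrawing without separately naming removal by the investigator. A reader might infer that the plan turns Hypothesis 3 into a completers' comparison by rule. The text does not support that; it happens only as far as the option is used. Still, nothing in the documents keeps a removed participant in testing.
- **Differential loss is not shown.** Session length and frequency (7.1), payment per training session (15.4) and tailoring of difficulty (8.2) are alike across arms. Similar loss in every arm would bias the contrast less. This stands: the documents establish neither the direction nor the size of any bias.
- **The reserve exists to absorb withdrawals.** A reader might cite a fall in power from 81% to 63% as a consequence of the plan. That needs a two-sided Dunnett test and all three arms at 7. The plan states neither, and its own one-sided t-test stays at about 82% at 7 per arm. This also stands. The reserve replaces numbers, however, and does not correct selection.
- **Retention has a cost for Hypothesis 4.** Partly trained participants can pull NT and TT together and so favour equivalence. This is correct, and the remedy has to deal with it.

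**Conclusion.** The concern holds in limited form. Sections 16.1 and 16.3 together allow balance training participants to be removed for missed sessions before their only Hypothesis 3 and 4 outcome is measured, with no threshold and no baseline balance-response measure. To the extent that the option is used and loss differs by arm, the comparison moves toward adherent completers.

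The illustrated shift of 0.6 to 2.8 degrees rests on assumed one-arm removal of 1 to 3 of 10 and an assumed correlation of 0.3 to 0.5; it vanishes at zero correlation. It is modest beside the 17.4-degree planning difference. Selective loss is the main issue and the sample size reserve a lesser one. A reader might also infer that giving up the sensors costs a balance training participant the lab test; the order of procedures in Section 8.1 rules that out.

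The change is worth making before enrolment, because the outcome of an untested participant cannot be recovered afterwards. Random allocation among TT, NT and ST is not stated explicitly, so the target is a comparison of the groups as assigned.

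**What to change.** - **Sections 16.1 and 16.3:** separate stopping training from leaving the study. For non-balance-training participants, do the same for stopping sensor wear. Invite every assigned participant to the lab session on schedule unless consent is withdrawn or testing would be unsafe. If removal by the investigator is kept, state the criterion in advance; its content is for the investigators to decide.
- **Section 5.2, Hypothesis 3:** make the analysis by assigned group primary and give a per-protocol analysis as a sensitivity analysis. State whether Dunnett's test is one-sided or two-sided.
- **Section 5.2, Hypothesis 4:** report both as-assigned and per-protocol equivalence results, because including partly trained participants can favour equivalence.
- **Reporting:** give sessions attended and removals, with reasons, by arm.

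The cost is protocol wording, lab sessions for participants who would otherwise have been removed, and slight dilution of the estimated training effect. At least ten per arm must still be recruited, since consent withdrawals will continue to cause some loss.

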17.0 Risks to Subjects

17.1 List the reasonably foreseeable risks, discomforts, hazards, or inconveniences to the subjects related to the subjects' participation in the research. Include for the IRB's consideration a description of the probability, magnitude, duration, and reversibility of the risks. Consider physical, psychological, social, legal, privacy, and economic risks. Do not indicate "No risk" or "N/A." Instead, for studies with very low risk (e.g., anonymous online questionnaire on a mundane topic) indicate "The investigators are not aware of any risks from participation in this study." or "No more than risks than are found in everyday life." The example consent form presents a tabular method for risk information, which you can also use here. Common risk types include:

- *Physical (e.g., potential for pain, discomfort, infection)*
- *Psychological (e.g., potential for stress, discomfort, and/or embarrassment)*
- *Social (e.g., potential for discrimination or stigmatization and disruption of personal and family relationships)*
- *Legal (e.g., potential for disclosure of illegal activity, negligence)*
- *Privacy (e.g., potential for personal information being accessed, used, or disclosed without the subjects' knowledge or consent, breach of confidentiality/security)*
- *Economic (e.g., potential for individuals to lose access to economic services, employment, insurability)*

21-1072 Validation and application of wearable sensors for capturing responses to losses of balance

There are potential risks for participants in the proposed work.

1. During a DEXA scan, participants will be exposed radiation. The amount of radiation is less than 2 days' exposure to natural background radiation (NBR). By comparison, a chest X-ray uses the equivalent of about 3 days' exposure to NBR, and a flight from UK to USA is equivalent to approximately a week's exposure to NBR (<https://www.nhs.uk/conditions/dexa-scan/#:~:text=The%20amount%20of%20radiation%20used,a%20week's%20exposure%20to%20NBR>).
2. During balance training or testing, there is a risk of muscle strains, joint strains, other soft tissue injury, or broken bones. The risk of these outcomes is considered low given our safety measures described in 17.2.
3. During balance training or testing, there is a risk of participants overexerting themselves. This risk is considered low given our safety measures described in 17.2.
4. During balance testing, the physical risk of skin irritation and bacterial exposure related to the reflective markers, lab-provided rubber soled shoes and clothing, as well as the safety harness, are very low (but not zero). We are not aware of a single incident of this in the PI's 20 years of conducting human subjects research.
5. After balance training or testing, there is the potential for participants to experience muscle or joint soreness. This risk is no different than participation in physical exercise, and is mitigated by the safety measures described in 17.2.
6. During the two-weeks of using wearable sensors, there is no more risk than is found in everyday life for losses of balance or falls because these sensors do not affect balance or fall risk.
7. In the event the wearable sensors are lost, stolen, or damaged during the course of the research, participants will not be held financially responsible for their replacement.

17.2 Indicate the measures you will use to minimize risks and monitor subjects for safety. (e.g., asking a subject at regular intervals to rate how they are feeling from 1 to 10, or to slowly crouch in order to check their balance.)

To minimize the risks described above in 17.1, the following safety measures will be used:

- a) using our medical screening process to exclude individuals at an increased risk of injury;

21-1072 Validation and application of wearable sensors for capturing responses to losses of balance

- b) having subjects complete warm-up exercises prior to balance training and testing including walking on a treadmill and stretching;
- c) the balance training used here was designed to be completed by adults 65-80 years;
- d) the balance training is tailored to each participant's capabilities;
- e) rest breaks will be provided as needed by the participant
- f) the same balance testing methodology employed here has been used in several of our prior studies without adverse outcome;
- g) an investigator and a spotter will be nearby participants to provide balance assistance, if necessary during balance training; and
- h) participants will wear a safety harness to prevent a fall to the floor during balance testing. The PI (who has extensive experience using the harnesses) will train the relevant study team member(s) in selecting the proper size safety harness, appropriately tightening all safety harness straps and connections, and setting the proper length of the lanyard that connects the harness to the overhead support. The harnesses we will be using are rated for individuals up to 310 lb, and we will limit our recruitment to individuals up to 250 lb.
- i) several measures will be taken to minimize the risk of skin irritation or bacterial exposure related to the reflective markers, lab-provided rubber soled shoes and clothing, as well as the safety harness, are very low (but not zero). These measures will include: a) using disinfecting wipes after each participant's testing, b) removal of adhesive material after each participant's testing, and c) using tape specifically designed to use on human skin.
- j) to minimize the exposure to radiation during DEXA scans, we will only use qualified study personnel to perform the scanning, and inform participants of the radiation exposure prior to scanning.

17.3 If applicable, indicate which procedures might have risks to the subjects that are currently unforeseeable. This will be rare, and usually applicable when testing a new drug or device or a new use of an existing drug or device:

N/A

17.4 If applicable, indicate which procedures might have risks to an embryo or fetus should the subject be or become pregnant:

21-1072 Validation and application of wearable sensors for capturing responses to losses of balance

N/A

17.5 If applicable, describe risks to others who are not subjects (e.g., collection of sensitive health data that might affect sexual partners if disclosed, mandatory reporting of abuse, DNA testing that might affect family members or relationships):

N/A

